3 STUDY DESIGN

This will be a single-center, triple-blinded, randomized controlled trial at the University of Michigan Health System, and approval has been obtained from the University Michigan Medical School IRB. The overall study flow is presented in the CONSORT⁴¹ Flow Diagram (Figure 2). As with our past studies, patients will be recruited at preoperative clinics, where informed consent will be obtained. Randomization methods will follow a stratified randomization model to match patients based on age and gender. Participants will be randomized with a 1:1 allocation ratio (placebo: caffeine) in a two-arm parallel design, and the randomization schedule and coding will be held by our hospital research pharmacy. Prepared intravenous piggyback solutions of 5% dextrose in water or caffeine citrate (200 mg caffeine) will be directly delivered to the operating room prior to the surgery of enrolled participants. The dose of 200 mg was chosen for two reasons: (1) this dose is in-line with similar clinical neurophysiology studies involving caffeine^{34,35,42,43} and (2) this has been the intraoperative dose used for safely preventing post-dural puncture/post-operative pain in surgical and obstetric patients. ^{22,29,32} In these studies, no significant side effects or adverse events were reported in relation to caffeine. This study will fulfill CONSORT guidelines⁴¹ for clinical trials as outlined in the following sections. Furthermore, this trial will be registered with www.clinicaltrials.gov prior to trial initiation, and all study team members will be certified in Good Clinical Practice as outlined by the NIH.

Assessment for **Enrollment** eligibility **Exclusions** Randomization Allocation Allocation to placebo (n=30) Allocation to caffeine (n=30) Analysis Analysis Anesthetic emergence time ◆ Anesthetic emergence time ◆ EEG power and connectivity · EEG power and connectivity ◆ Trail Making Test ◆ Trail Making Test · Postoperative opioid use Postoperative opioid use • Postoperative pain assessments · Postoperative pain assessments Delirium assessments · Delirium assessments Depression, anxiety scales • Depression, anxiety scales ◆ Affect questionnaire ◆ Affect questionnaire ◆ 30-day follow-up health survey ◆ 30-day follow-up health survey

Figure 2: Planned study flow diagram based on Consolidated Standards of Reporting Trials (CONSORT)

Planned study flow diagram based on Consolidated Standards of Reporting Trials (CONSORT).⁴¹ EEG = electroencephalogram

Inclusion criteria: Adult (≥18 years old) patients undergoing non-cardiac, non-neurologic, non-major vascular surgery (i.e., below the diaphragm).

Exclusion criteria: Emergency surgery, cognitive impairment precluding capacity for informed consent, uncontrolled cardiac arrhythmias, seizure disorders, intolerance or allergy to caffeine, history of diabetes, preoperative opioid use, pheochromocytoma, acute liver failure, enrolled in conflicting research study, pregnancy, breastfeeding, severe visual or auditory impairment (may hinder cognitive function testing), and patients unable to speak English.

Perioperative and anesthetic procedures: Patients will be consented and enrolled at preoperative clinic locations, where a medical and psychiatric history will be taken and baseline assessments will be administered (described further below). After enrollment, patients will also complete a caffeine intake survey to quantify baseline caffeine consumption. On the day of surgery, baseline cognitive function testing (TMT) will take place in the preoperative holding area. Subsequently a 16-channel wireless EEG system (Cognionics, Inc.) will be applied to the scalp for continuous monitoring during surgery and the perioperative period. Once in the operating room, anesthetic induction and maintenance will proceed as deemed clinically appropriate by the anesthesia team. At the beginning of surgical closure, the study drug will be given via intravenous infusion over 60 minutes (placebo vs. caffeine, 200 mg) in a triple-blinded fashion: the anesthetic team, research staff, and patient will all be blinded to the intervention. Infusion of this dose over a 60-minute period has been safely described, without significant side effects or adverse events noted.^{28,32} A member of the research team will remain in the operating room to monitor drug infusion and collect data regarding timing of anesthetic discontinuation and emergence; this will aid methodological rigor and data validation for the study. The EEG sensors will remain in place during the operation and emergence from anesthesia; they will then be removed shortly after PACU arrival. One hour after the caffeine infusion finishes, pain and cognitive function measures will be assessed.

Pain and sleep assessments: Inpatient opioid consumption will be monitored from the first PACU assessment through postoperative day three (or discharge, whichever occurs sooner) (primary outcome). Subacute opioid consumption (postoperative days 4-7) will be calculated as an additional outcome. All opioids will be converted to oral morphine equivalents (mg), and intraoperative opioid administration will be calculated as well and compared between groups. Pain measures will include the 10 centimeter Visual Analog Scale (VAS)⁴⁴ and Behavioral Pain Scale (BPS)⁴⁵ for subjective and objective pain assessment, respectively. Assessments will begin 1 hour after caffeine infusion has finished (once patient is in the PACU), and they will continue twice daily (morning and afternoon) for the first three postoperative days. Preoperatively, the Richards-Campbell Sleep Questionnaire (RCSQ)⁴⁶ will be administered to determine self-reported sleep quality the previous evening. As an additional outcome, self-reported sleep disturbances will also be assessed during these daily pain assessments (i.e., from the PACU through postoperative day 3).

EEG data acquisition: Our research group has extensive experience with EEG data acquisition and analysis in human volunteers^{47,48} and surgical patients.^{49,50} We have

demonstrated feasibility with collecting whole-scalp, 16-channel wireless EEG data (Cognionics, Inc.) in 50 surgical patients. Representative spectral and connectivity data are presented in Figure 3. Our group will use this same EEG technology to collect and analyze data for the proposed study. Spectral power (decibels, DB) and connectivity (phase lag index, PLI) data will be collected and analyzed during anesthetic emergence and PACU arrival.

[figure not shown]

Figure 3: Representative wireless EEG data from a surgical patient

Example wireless perioperative EEG data obtained from a related study (R01GM098578). LOC = loss of consciousness, PACU = postanesthesia care unit, dB = decibels, PLI = phase lag index (an EEG measure of functional connectivity).

Neurocognitive assessments: Time from surgical closure to anesthetic emergence will be calculated by the study team. (minutes). The Trail Making Test will be used to assess perioperative cognitive function. The TMT is a validated, reliable test that assesses four cognitive domains relevant to the perioperative setting: processing speed, attention, visual scanning, executive function, and working memory. The TMT is administered in a standardized fashion using paper and pencil and takes approximately 5 minutes to complete. This is a feasible strategy in the perioperative setting to obtain comprehensive cognitive function data (e.g., attention, executive function) in a relatively short period of time, and normalized population data are available for comparisons. The test will be administered preoperatively and one hour after the caffeine infusion has completed in conjunction with pain assessments. Changes (n) in standardized scores from baseline will be calculated, and final standardized scores (n) will also be calculated and reported in the event that baseline scores are unable to be obtained (given the time-constraints present in the preoperative setting, it might not be possible to achieve baseline cognitive function scores in all patients).

Neuropsychological assessments: The Hospital Anxiety and Depression Scale (HADS)³⁸ will be used to assess for active depression and anxiety symptoms in each group. These assessments will take place at baseline and after the last inpatient assessment on postoperative day 3. Scores ≥8 for the anxiety (HADS-A) and depression (HADS-D) subscales will be considered positive screens.⁵¹ The Positive and Negative Affect Schedule

(PANAS)³⁹ will be used to characterize mood and affect at the same time points as depression and anxiety screening (baseline and postoperative day 3). The *Confusion Assessment Method (CAM)* will be used to assess for delirium throughout the first three postoperative days using previously described methods.^{14,40} Lastly, a follow-up health and well-being survey will be sent to participants thirty days after surgery. This survey will include the Veterans RAND 12 Item Health Survey (VR-12, continuous measure).⁵² Presence of persistent opioid use (yes/no, binary) will also be asked in this thirty-day survey.

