2.2 Endpoints

2.2.1 Primary Endpoint

Cumulative opioid consumption (mg) through postoperative day 3 (or discharge, whichever is sooner.

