6.2 Treatment Study Period

6.2.1 Visit 1 (Day 1)

As outlined in the above protocol, visit 1 (day 1) will be the day of scheduled surgery. During this time, a preoperative pregnancy test will first be drawn as clinically indicated. Vitals will be taken throughout the perioperative period per clinical guidelines and protocols. The RCSQ will be administered to assess sleep quality the prior evening. Baseline Trail Making Test (TMT) scores will be collected. The wireless EEG cap will then be placed preoperatively, and EEG monitoring will then commence perioperatively under supervision of the study team. A member of the study team will then receive the study drug from the research pharmacy, which will prepare the drug per block randomization protocol. The study team will then administer this during (one-hour infusion) at the beginning of surgical closure. The EEG cap will be removed after postanesthesia care unit (PACU) arrival, and one hour after the infusion has finished, the study team will perform the designated research study assessments (i.e., pain assessments, cognitive function testing, and Quality of Recovery (QoR) questionnaire). Intraoperative and PACU opioid data will also be tabulated.

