6.2.3 Follow-up (Postoperative Days 4-7)

During this time, opioid consumption and caffeine intake assessments will be obtained over the telephone. Adverse events will continue to be monitored.

SCHEDULE OF ACTIVITIES

	Screen	Visit 1 Day 1	Visit 2 Day 2	Visit 3 Day 3	Visit 4 Day 4	Phone call Days 5-7	Day 30
Protocol Activity		Day of Surgery	POD1	POD2	POD3	POD4-7	
Visit (POD1-3) /Phone call (POD4-7)	-	X	X	X	X	X	
Informed consent	X						
Medical history	X						
Vitals*	X	X	X	X	X		
Depression, Anxiety, and Affect Scales	X			X			
Serum pregnancy test		X					
Randomization		X					
Treatment with study agent		X					
Opioid use assessments		X	X	X	X	X	
Cognitive function testing	X	X^{\dagger}					
Pain/sleep assessments [‡]	X	X	X	X	X		
Caffeine intake assessment	X		X	X	X	X	
EEG assessments		X			·		
Adverse event assessment	_	X	X	X	X	X	
Health and well-being survey							X

^{*} Vitals will be recorded per clinical protocol on each respective ward/ICU. †Second cognitive function testing session will occur in the postanesthesia care unit ‡Pain and sleep assessments will occur and twice daily (morning and afternoon) from POD1-3; the RCSQ in particular will be administered on Day 1, preoperatively. Pain assessments will also be taken once in the postanesthesia care unit prior to the cognitive function assessment. POD = postoperative day, TMT = trail making test, EEG = electroencephalogram

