9.2.3 Analysis of Primary Endpoint

A generalized linear mixed model will be the primary analytic tool with appropriate datadriven choice of the link function. Linear regression will be used for assessing cumulative opioid consumption through postoperative day three. A separate analysis will entail longitudinal modeling with repeated oral morphine equivalent (OME) measurements (i.e., we will analyze multiple points of the OME curve simultaneously). A Gaussian subjectspecific intercept term will be included to model between-subject differences and the associated correlation structure. The Time variable (main effect, baseline, PACU, POD1-3) will be used to model the pattern of the respective outcome variable (response) over time in the placebo group. The Group variable (an indicator of the caffeine group, main effect) is an indicator of whether the subject received the caffeine intervention. The Group by Time interaction term expresses the differences of caffeine vs. placebo as far as the pattern of response over time is concerned. Final results will be assessed based on the best model selected using Likelihood Ratio tests and Akaike Information Criteria (AIC). In addition to the model specified above, a models will be constructed a) containing the above group and time specification with the addition of demographic variables and b) containing (a) with the addition of intraoperative factors.

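### The only stated start of the primary opioid total is a research assessment about 120 minutes after closure begins; read literally, it leaves early postoperative opioid uncounted and conflicts with other sections

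*Combined protocol and SAP*

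**What the plan says.** The formal endpoint in section 2.2.1 is "Cumulative opioid consumption (mg) through postoperative day 3", or to discharge if sooner. Section 7.1 repeats the end of the window. Neither section gives a start.

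Section 3 (Pain and sleep assessments) supplies one, in the sentence labelled as the primary outcome: "Inpatient opioid consumption will be monitored from the first PACU assessment through postoperative day three". The same paragraph makes intraoperative opioid a separate comparison between groups.

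The timing of the PACU assessment follows from three statements:

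- Section 3, perioperative procedures: "At the beginning of surgical closure, the study drug will be given via intravenous infusion over 60 minutes".
- Section 3, pain assessments: "Assessments will begin 1 hour after caffeine infusion has finished (once patient is in the PACU").
- Section 6.2.1: "one hour after the infusion has finished, the study team will perform the designated research study assessments".

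A footnote to the Schedule of Activities adds "Pain assessments will also be taken once in the postanesthesia care unit prior to the cognitive function assessment". It gives no hour.

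Two other places handle PACU opioid without any cut at the one-hour assessment. Section 6.2.1 says "Intraoperative and PACU opioid data will also be tabulated". Section 9.2.3 lists the levels of the longitudinal model: "The Time variable (main effect, baseline, PACU, POD1-3").

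**The concern.** A cumulative endpoint needs a defined start as well as a defined end. The only start given here is the time of a research assessment, not a clinical event, and that assessment comes well after the patient has left surgery. Opioid given in the meantime is no longer intraoperative and, on the literal wording, not yet part of the primary total.

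The interval matters because it covers emergence and the first treatment of acute pain, just as the study drug has been given. If caffeine lowers opioid need early, a window that opens later would not show it.

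The interval may also differ between arms in how much awake, treated time it holds. Section 2.1 hypothesizes that caffeine speeds recovery from anesthesia. If so, patients on caffeine would spend more of the period before counting opens awake and able to receive opioid for pain.

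Finally, the sections disagree. One analyst following section 3 would start partway through the PACU stay. Another following sections 6.2.1 and 9.2.3 would count all of it.

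**Working it through.** **1. The plan's own power figure.** Inputs from section 9.1: means 0.7 and 6.5, SDs 3 and 10, N = 60, two-sided t-test with unequal variances. Allocation is 1:1, so 30 per arm. Alpha is not stated in that section; 0.05 is assumed.

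- Difference: 6.5 − 0.7 = 5.8
- Standard error: √(3²/30 + 10²/30) = √(109/30) = 1.906
- Noncentrality: 5.8 / 1.906 = 3.04, with Satterthwaite df = 34.2
- Power from the noncentral t distribution: 84.0%, against 83% stated

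The figure reproduces to within about one point. Its inputs are opioid values on postoperative day 1, so they do not contain the interval in question. The calculation is the same whichever start is used.

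**2. When counting opens on the literal reading.** Infusion length is 60 min from the beginning of closure, and the assessment is 60 min after the infusion ends:

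60 + 60 = 120 min after closure begins.

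**3. How much PACU time falls before that.** The documents do not give the time from closure to PACU arrival, so a range is assumed. Uncounted PACU time = 120 − arrival time.

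| Assumed PACU arrival (min after closure begins) | PACU time before counting opens (min) |
|---|---|
| 30 | 90 |
| 45 | 75 |
| 60 | 60 |
| 90 | 30 |

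Opioid given between the end of surgery and PACU arrival comes on top of this, unless the intraoperative total is meant to run to PACU hand-over. The documents do not say where that total ends.

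**4. Effect on the endpoint.** This would need the opioid dose given in the interval, by arm. The documents give none, so it cannot be computed.

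**5. The sections side by side.**

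| Section | Start of primary total, or handling of PACU opioid |
|---|---|
| 2.2.1 and 7.1 | No start |
| 3 | First PACU assessment |
| 6.2.1 | PACU opioid tabulated as a whole |
| 9.2.3 | PACU as one undivided time level |

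**6. Ward opioid on the evening of surgery.** The section 3 window is continuous, so this opioid is inside the cumulative endpoint. In the longitudinal model, the listed levels go from PACU to postoperative day 1. Opioid given after PACU discharge but before day 1 has no stated level, so the levels need not add up to the cumulative total.

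**The case against.** The strongest reply is that this is a loose phrase and not an exclusion. The formal endpoint has no start that would leave early PACU opioid out. The Schedule of Activities marks opioid assessment for the day of surgery. Section 6.2.1 collects PACU opioid without a cut, and section 9.2.2 relies on inpatient medication administration records, which do not depend on a research visit. The one-hour statement in section 3 follows the description of the pain scales and may time only those. The first PACU assessment is nowhere expressly defined as the one-hour visit for the purpose of counting opioid.

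Much of this stands. A reader might infer that the plan has decided to drop early PACU opioid. The documents do not support that: it is the literal reading of one sentence, and other sections point the other way. The reply does not remove the conflict, though. The other sections show that the data will exist, not that they enter the primary total, and no earlier PACU assessment is described.

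A reader might also infer that evening ward opioid is missing from the primary endpoint. It is not, because the window in section 3 runs without a break to postoperative day 3. Only the longitudinal model, which section 9.2.3 calls a separate analysis, lacks a place for it.

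Nor is bias shown. The same rule applies to both randomized arms, and the literal start is about 120 minutes after infusion start in each patient, apart from staff timing. A late start means lost sensitivity to an early effect, or a different quantity being estimated. A difference between arms through faster emergence is possible, but the documents give nothing to measure it with.

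**Conclusion.** The start of the primary opioid total is inconsistently specified. On the natural reading of its only stated start, counting opens about 120 minutes after closure begins, and opioid given from the end of surgery to that point is in neither the intraoperative nor the primary total. With PACU arrival assumed at 30 to 90 minutes after closure begins, this covers the first 90 to 30 minutes in the PACU.

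The size in milligrams is unknown, and its direction by arm cannot be established from the documents. It would be wrong to conclude that the trial loses power: the stated 83% rests on postoperative day 1 values and holds under either reading.

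The conclusion rests on taking the first PACU assessment to be the one-hour research assessment, which is the natural but not the express meaning. Severity: should-fix.

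**What to change.** **Primary endpoint (sections 2.2.1, 3 and 7.1).** State one start in all three places: a fixed clinical time read from the medication administration record, preferably the end of surgery. Let the intraoperative total end at the same time, so that the two totals are contiguous.

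The end of surgery is a better choice than PACU arrival for two reasons. A PACU-arrival start would still omit opioid given between emergence and arrival. Arrival time may also itself be affected by caffeine, since the protocol hypothesizes faster emergence. The end of surgery is tied neither to these nor to the timing of the research visit.

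**Longitudinal model only (sections 6.2.1 and 9.2.3).** Define the day-of-surgery level to run from that same start to the start of postoperative day 1, and state when day 1 begins. Evening ward opioid then has a level, and the levels sum to the cumulative total.

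**Cost.** Wording in five sections. The data come from the inpatient medication administration records that section 9.2.2 already relies on. No added visit, patient or change to the sample size is needed. The wording should be settled before unblinding, so that the choice of start cannot depend on results.

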2.2.2 Secondary Endpoint*

- VAS, n, PACU and postoperative days 1-3 (twice daily)
- BPS, n, PACU and postoperative days 1-3 (twice daily)
- Time until anesthetic emergence (min)
- Delirium incidence (%)
- Positive depression screen incidence (%)
- Positive anxiety screen incidence (%)
- Change in affect scores (n)
- Change in Trail Making Test scores (n) from baseline

^{*}Tertiary assessments are listed in section 7.2

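### The schedule marks a screening pain/sleep assessment that the text does not describe, and no adjustment for baseline pain is prespecified

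*Combined protocol and SAP*

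**What the plan says.** **Schedule.** The Schedule of Activities (after Section 6.2.3) has one combined row, "Pain/sleep assessments", marked at Screen, Visit 1 and postoperative days (POD) 1, 2 and 3. Its footnote gives the timing as twice daily on POD1-3 and then adds: "the RCSQ in particular will be administered on Day 1, preoperatively. Pain assessments will also be taken once in the postanesthesia care unit". It assigns nothing to Screen.

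**Text.** Section 3 (Pain and sleep assessments) says of VAS and BPS: "Assessments will begin 1 hour after caffeine infusion has finished (once patient is in the PACU". Section 6.2.1 lists pain on Day 1 only after the infusion, and Section 6.2.2 lists it on POD1-3. Section 2.2.2 defines the endpoint as "VAS, n, PACU and postoperative days 1-3 (twice daily"), with no baseline, while the cognitive endpoint in the same list is "Change in Trail Making Test scores (n) from baseline". Section 3 also says that at the preoperative clinic "baseline assessments will be administered (described further below"), but no preoperative VAS or BPS is described afterwards.

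**Analysis.** Section 9.2.3 states: "The Time variable (main effect, baseline, PACU, POD1-3) will be used to model the pattern" of the respective outcome. Its extended models add demographic variables and then intraoperative factors. Section 9.2.2 admits to the multivariable models any measure whose standardized difference between arms exceeds 0.1. Section 9.2.4 uses a t-test or Mann-Whitney test for continuous secondary endpoints, with modelling like the primary's where appropriate.

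**The concern.** Staff who follow the schedule and staff who follow the text would collect different data. A preoperative score that was not taken cannot be recovered after surgery.

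The population has mixed operations (Section 4.1.1). Preoperative opioid use is excluded, but preoperative pain is not, and stratification is by age and gender only (Section 3). Starting pain may therefore vary between patients and may explain part of the variation in postoperative VAS, and perhaps in opioid use. If no score is taken, or one is taken without a prespecified role, that information is lost in a trial powered on 60 patients.

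The unclear baseline level also affects what the longitudinal model estimates. If baseline is the reference level of Time, the Group main effect is a preoperative difference, which is zero in expectation under randomization. If that level is empty, the reference moves to a later time and the same coefficient means something else.

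**Working it through.** **1. Is the Screen mark real?** The text was machine-read, so the alignment needs checking. The rows for opioid use, randomization and EEG keep an empty Screen cell, while the pain/sleep row has a mark there. The mark therefore appears to belong to Screen.

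**2. Which instrument could it refer to?**

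| Instrument | Where the text and footnote place it | At Screen? |
|---|---|---|
| VAS, BPS | PACU, then POD1-3 (Sections 2.2.2, 3, 6.2.1, 6.2.2, footnote) | No |
| RCSQ | Day 1, preoperatively (Section 6.2.1, footnote) | No |
| Self-reported sleep disturbance | PACU to POD3 (Section 3) | No |

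No described instrument fits. The RCSQ asks about the previous night, and screening may be days to weeks before surgery (Section 6.1).

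**3. What stands behind the baseline time level?** For pain, no measurement is defined. For oral morphine equivalents (OME), Section 3 starts the count at the first PACU assessment and Section 4.1.2 excludes preoperative opioid use, so a baseline value is undefined or near zero.

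**4. Does the imbalance rule supply the adjustment?** It can act only on a score that was collected. With 30 per arm, the standard error of a standardized difference is about √(2/30) = 0.26. A randomized baseline variable then exceeds 0.1 in absolute value about 70% of the time by chance, prognostic or not. Entry would depend on chance and not on a prior decision.

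**5. The plan's own power figure.** Inputs from Section 9.1: means 0.7 and 6.5 (difference 5.8), SDs 3 and 10, N = 60 (30 per arm), two-sided unequal-variance t-test. Alpha is not stated; 0.05 is assumed.

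- Standard error = √(3²/30 + 10²/30) = √(0.300 + 3.333) = 1.906
- Noncentrality = 5.8/1.906 = 3.04, with Satterthwaite df = 34.2
- Power = 0.840, against the stated 83%: reproduced, with no baseline covariate involved.

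**6. What adjustment could add.** A covariate with correlation r to the outcome multiplies residual variance by 1 − r². The equivalent gain in sample size is 1/(1 − r²) − 1. The documents give no r, so a range is assumed. The power column repeats step 5 with both SDs multiplied by √(1 − r²). This is an approximation that assumes the same r in both arms and ignores the degree of freedom spent.

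| Assumed r | Variance removed | Equivalent extra patients | Power, Section 9.1 inputs |
|---|---|---|---|
| 0 | 0% | 0% | 0.840 |
| 0.2 | 4% | 1/0.96 − 1 = 4% | 0.855 |
| 0.3 | 9% | 1/0.91 − 1 = 10% | 0.873 |
| 0.5 | 25% | 1/0.75 − 1 = 33% | 0.927 |

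The power column applies to the opioid outcome and is illustrative. The documents give no SD for VAS, so only the variance and sample-size columns apply to it.

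**The case against.** The strongest reply is that this is one stray mark in a combined row. The schedule seems to use Screen loosely for anything preoperative: cognitive testing is also marked there, with the PACU test called the second session, although Sections 3 and 6.2.1 put the baseline test on the day of surgery. On that habit, the mark may mean only the preoperative RCSQ. The table may also be misread elsewhere, since the depression, anxiety and affect row shows POD2 where the text says POD3. This stands in part. A reader might infer that a preoperative VAS is planned and then discarded, and the documents do not establish that. They leave the question open, and the footnote does not settle it.

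Other stronger readings also fail:

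- **That the secondary analysis requires a preoperative pain value.** Section 9.2.4 makes modelling optional, and a similar model could start at the PACU.
- **That baseline pain could never enter a model.** If collected, it could enter through the imbalance rule in Section 9.2.2. The accurate statement is that its use is not prespecified.
- **That VAS is the leading secondary endpoint.** It is listed first, but the list is not ranked.
- **That omitting baseline pain biases the comparison.** Allocation is randomized 1:1, so it does not.

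It is also fair to say that the gain rests wholly on assumed correlations and is small at the low end. At r = 0.2 the illustrative power rises by about 1.5 percentage points.

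**Conclusion.** The inconsistency is real but narrow: the Screen mark has no described instrument, so whether a preoperative pain score exists is unclear. Separately, no adjustment for baseline pain is prespecified for VAS or for opioid consumption, and the baseline time level in Section 9.2.3 is undefined for pain and uninformative for opioids.

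The consequence is possible lost precision. Its size depends on a correlation the documents do not supply: negligible at 0.2 or below, moderate at 0.3, and material only towards 0.5. The case is better for VAS, where baseline and outcome are the same measure, than for opioid use, where the adjustment is optional. The power calculation in Section 9.1 stands on its own inputs, with alpha of 0.05 assumed. This is a cheap improvement and a needed clarification, not a flaw that threatens the trial's validity.

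**What to change.** 1. Make Section 3, Section 6.2.1 and the Schedule of Activities agree on one preoperative VAS, for example in preoperative holding on Day 1 with the RCSQ and Trail Making Test. Move or remove the Screen mark and name the instrument in the footnote.
2. In Section 9.2.4, prespecify that score as a continuous covariate in the postoperative VAS analysis, with time levels PACU and POD1-3. Optionally, add it to the linear regression of cumulative OME in Section 9.2.3.
3. In Section 9.2.3, define the baseline time level for each outcome or drop it, and state the reference level so that the Group coefficient has one meaning.
4. State how a missing preoperative score will be handled. Section 3 already warns that time constraints may prevent baseline cognitive testing in some patients, and the same could happen here.

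The cost is one VAS mark per patient at a contact staff already attend, some missing values, and a few sentences of protocol and SAP text. If the sponsor prefers not to collect the score, the Screen mark and the baseline time level still need correcting.
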